Figure 1. Operational Steps to Identify Cases and Exposure Information for the SCRI, CCO, and Vaccinated Case-Coverage Designs 20

Figure 3-1. Self-controlled Risk Interval Design 41

Figure 3-2. Case-Crossover Study Design 43

2 List of Abbreviations

ACCESS	vACcine Covid-19 monitoring readinESS
AESI	adverse event of special interest
CCO	case-crossover
CDM	common data model
COVID-19	illness caused by the SARS-CoV-2 virus
CRF	case report form
EMA	European Medicines Agency
ENCePP	European Network of Centres for Pharmacoepidemiology and Pharmacovigilance
EU PAS Register	European Union Electronic Register of Post-Authorisation Studies
GPP	Good Pharmacoepidemiology Practices
GVP	Good Pharmacovigilance Practices
ISPE	International Society for Pharmacoepidemiology
SARS-CoV-2	severe acute respiratory syndrome coronavirus 2
SCCS	self-controlled case series
SCRI	self-controlled risk interval
WHO	World Health Organization

3 Responsible Parties

To be completed by study investigator(s):

[Principal investigator institution name]

Address

name, degrees, job title

name, degrees, job title

name, degrees, job title

name, degrees, job title

name, degrees, job title

name, degrees, job title

[Sponsor name]

Address

name, degrees, job title

name, degrees, job title

name, degrees, job title

name, degrees, job title

name, degrees, job title

name, degrees, job title

Collaborating Institutions

Study Sites

4 Abstract

This section should be filled out with the following information.

Title:

Rationale and background:

Research question and objectives:

Study design:

Population:

Variables:

Data sources¹:

Study size:

Data analysis:

Milestones²:

¹ Database custodians and research partners will be contacted to explore interest in and availability to participate in the study.

² Contracts between the sponsor and research organisation(s) and approvals by data protection, data custodian, ethics, and scientific review bodies are pending. Timelines may be impacted by approvals of these bodies, duration of contract reviews, and availability of data and staff at research institutions once contracts and approvals are finalised.

5 Amendments and Updates

None to date.

6 Milestones and Timeline

This section should be filled out with the following information.

Milestone	Date
Start of data collection ^a	
End of data collection ^b	
<Study progress report(s) 1>	
<Study progress report(s) 2>	
<Study progress report(s) 3>	
<Interim report 1>	
<Interim report 2>	
<Interim report 3>	
<Registration in the EU PAS Register>	
Final report of study results	

EMA = European Medicines Agency; EU PAS Register = European Union Electronic Register of Post-Authorisation Studies.

Note: Contracts between the sponsor and research organisation(s) and approvals by data protection, data custodian, ethics, and scientific review bodies are pending. Timelines may be impacted by approvals of these bodies, duration of contract reviews, and availability of data and staff at research institutions once contracts and approvals are finalised.

^a Start of data collection is “the date from which information on the first study subject is first recorded in the study data set or, in the case of secondary use of data, the date from which data extraction starts.” [1]

^b End of data collection is “the date from which the analytical data set is completely available.” [1]

7 Rationale and Background

The novel coronavirus SARS-CoV-2, the cause of COVID-19, has led to a global pandemic. Several COVID-19 vaccine candidates are currently under research and in development. COVID-19 vaccines may be licensed by the European Medicines Agency (EMA) after thorough review of data on quality, efficacy, and safety. Because the prelicensure period is short and the number of participants in clinical studies may be too small to enable the detection of extremely rare events, efficient monitoring of vaccine safety in the postmarketing phase will be needed, with the objective of identifying as rapidly as possible any unintended side effects of vaccination. Because it is likely that a large number of individuals would be vaccinated against COVID-19 as a preventive measure, it is crucial to detect even rare serious adverse events shortly after licensure.

As part of its preparedness activities, the vACcine Covid-19 monitoring readinESS (ACCESS) project has developed several template protocols that address vaccine coverage, vaccine effectiveness, and vaccine safety. To allow all countries to participate and to use maximum capacity in Europe, protocols are divided into those that use primary data collection (hospital based) and those that rely on the secondary use of population-based electronic health records databases.

This template protocol provides a framework for designing a hospital-based study to examine the risk of prespecified adverse events following COVID-19 vaccination using a self-controlled or other case-based study design. The template protocol may be used to investigate adverse events of special interest (AESI) (hypothesis generation), but the principles described can be applied to the study of unanticipated adverse events (signal evaluation). The ACCESS protocol templates based on secondary use of population-based electronic health records databases require those types of data to identify the study population, exposures, and outcomes. In contrast, this protocol template does not require data for the full source population or the use of population-based registers; the approach involves the recruitment of individual hospital sites. Hospital sites will identify eligible cases that have been treated at the hospital (whether in inpatient, emergency department, or outpatient ambulatory care) using locally held electronic records (e.g., discharge databases) and collect additional data from other sources (e.g., medical records, vaccination cards). This template will allow countries or other geographic locations that do not have population-based registers to participate in COVID-19 vaccine safety studies in a valid and efficient manner.

Irrespective of whether a signal has been identified, AESI are proposed as high priorities for assessment because they represent potential risks that would need immediate investigation or regulator action, based on experience with the specific vaccine being monitored or similar vaccines in terms of manufacturing process, composition (e.g., adjuvants), immunogenicity, and novelty.

As part of the harmonisation of COVID-19 vaccine safety monitoring during the clinical development phase, the Coalition for Epidemic Preparedness Innovations (CEPI) and the

Brighton Collaboration have created a preliminary list of AESI for COVID-19 vaccine safety monitoring [2]. Within the ACCESS project, a list of AESI was created and was approved by the EMA (EUPAS37273), as follows. The listed AESI may not become real safety concerns, but this template provides a framework to evaluate them. Additionally, the principles and study designs described in this protocol template may be used to address potential unexpected safety signals that may arise during product development or after licensure.

- Enhanced disease following immunisation
- Multisystem inflammatory syndrome in children
- Acute respiratory distress syndrome
- Acute cardiovascular injury, including microangiopathy, heart failure, stress cardiomyopathy, coronary artery disease, arrhythmia
- Coagulation disorder, including deep vein thrombosis, pulmonary embolus, cerebrovascular stroke, limb ischaemia, haemorrhagic disease
- Generalised convulsion
- Guillain Barré syndrome
- Diabetes (type 1 and unspecified type)
- Acute kidney injury
- Acute liver injury
- Anosmia, ageusia
- Chilblain-like lesions
- Single organ cutaneous vasculitis
- Erythema multiforme
- Anaphylaxis
- Death (any cause)
- Sudden death
- Acute aseptic arthritis
- Meningoencephalitis
- Acute disseminated encephalomyelitis
- Narcolepsy
- Thrombocytopenia
- Transverse myelitis
- Fetal and pregnancy outcomes (preterm birth, major congenital anomalies, microcephaly, fetal growth restriction, gestational diabetes, preeclampsia, spontaneous abortion, stillbirth, induced abortion, termination of pregnancy for fetal anomaly, neonatal death, maternal death)

Historically, vaccine safety studies have often used self-controlled designs such as the self-controlled case series (SCCS) and its variant, the self-controlled risk interval (SCRI) design, and the case-crossover (CCO) design because they make comparisons between exposed versus unexposed person-time within the same individual, rather than between exposed and unexposed individuals. Because of this, self-controlled designs inherently adjust for time-invariant confounders (both measurable and unmeasurable), such as chronic conditions present before the start of the follow-up period that are associated with the likelihood of vaccination (due to the increased risk of complications due to the disease vaccinated against) and adverse events under study. These designs are appropriate for studying the effect of transient exposures on outcomes that have acute onset and short latency, a short induction period (i.e., the outcome occurs within days or weeks of exposure), and a hypothesised period of increased risk (referred to as “risk windows”) following exposure. Self-controlled designs are useful when coverage rates of immunisation are high, which makes it difficult to identify an appropriate comparator [3]. Only vaccinated individuals who have experienced an event are informative to risk estimation in the SCRI and CCO designs; thereby avoiding bias due to exposed persons being wrongly classified as unexposed because the data source for vaccinations is incomplete, and due to confounding by indication or contraindication [4]. Finally, because the SCRI and CCO designs both include in risk estimation only vaccinated persons who have experienced an event, no separate controls are required, and capture of all events in the population is not required [4].

Three designs have been identified as appropriate for use in a case-based hospital setting: the SCRI with a postvaccination control interval, the CCO, and vaccinated case-coverage designs. A vaccinated case-coverage design, a variant of the case-coverage design proposed in this template, will use the distribution of vaccine exposures in a population of persons similar to the cases to adjust for time trends in exposure present in a CCO design. An overview of each design as well as its assumptions, requirements, strengths, and limitations within the context of hospital-based studies are described in Annex 3.

Only AESIs that are typically treated in the hospital (inpatient, outpatient specialist, or emergency department) are appropriate to study with the approaches described in this template. Based on the assumptions and requirements of each proposed design, Table 1 comprises a decision framework for determining when the SCRI (with postvaccination control interval), CCO, and vaccinated case-coverage design can be used to study the specific AESIs with this protocol template. The framework takes into consideration outcome and vaccination characteristics, including the outcome latency and onset, ability to define the risk period for outcome following vaccination, effect of the outcome on likelihood of vaccination, and presence of temporal trends in vaccination. Annex 4 describes which of the AESIs are suitable to be studied using each of the three designs using outcome-based criteria. In addition to AESIs, unanticipated adverse events for which signals arise during clinical development or postlicensure can be assessed for

suitability of use of the SCRI, CCO, or vaccinated case-coverage design based on the full decision framework.

Table 1. Decision Framework for Determining Suitability of the SCRI, CCO, or Vaccinated Case-Coverage Design^a

Criteria	Suitability of the SCRI (Postvaccination Control Window)	Suitability of the CCO	Suitability of the Vaccinated Case- Coverage Design
Outcome is treated in the hospital			
Yes	✓	✓	✓
No	✗	✗	✗
Outcome latency			
Short latency	✓	✓	✓
Long latency	✗	✗	✗
Outcome onset			
Acute onset	✓	✓	✓
Gradual onset	✗	✗	✗
Ability to define risk period for outcome following exposure			
Can be clearly defined	✓	✓	✓
Cannot be clearly defined	✗	✗	✗
Effect of outcome on likelihood of vaccination			
Outcome does not affect likelihood of vaccination	✓	✓	✓
Outcome temporarily decreases or increases likelihood of vaccination and the vaccine is a single dose	✓	O ^b	O ^b
Outcome temporarily decreases or increases likelihood of vaccination and the vaccine is multidose	O ^c	O ^b	O ^b
Outcome is a (permanent) contraindication to vaccination and the vaccine is single dose	✓	O ^b	O ^b
Outcome is a (permanent) contraindication to vaccination and the vaccine is multidose	O ^c	O ^b	O ^b
Outcome censors the period of observation for exposure (e.g., the outcome is death)	O ^d	✓	✓
Recurrence of outcome			
Outcome is independently recurrent	✓	✓	✓
Outcome is non-recurrent but rare	✓	✓	✓

Criteria	Suitability of the SCRI (Postvaccination Control Window)	Suitability of the CCO	Suitability of the Vaccinated Case- Coverage Design
Outcome is recurrent, and recurrent events are not independent (e.g., stroke)	✓ ^e	✓	✓
Temporal trends in vaccination			
Temporal trends in vaccination are not present during the study period	✓	✓	✓
Temporal trends in vaccination are present during the study period	✓	X	✓

CCO = case-crossover; SCRI = self-controlled risk interval.

Key: Checkmark (✓) indicates design is suitable; X indicates not suitable; O indicates that the study design is possible under certain circumstances.

^a Adapted from Baker et al. [4], Petersen et al. [5], and Madigan et al. [6].

^b Suitable if prodromal symptoms before diagnosis of the outcome do not cause or prevent vaccination, either temporarily or permanently. To address this potential source of bias, every effort should be made to identify the onset of symptoms from the available data such as medical records, rather than relying on the date of diagnosis.

^c The impact of bias due to the potential interference of the outcome on subsequent vaccination could be explored using Farrington’s pseudolikelihood method for censored, perturbed, or curtailed postevent exposures [7].

^d Farrington’s pseudolikelihood method for censored, perturbed, or curtailed postevent exposures should be used to address bias due to censoring of exposures by events [7].

^e If the event can be recurrent, and recurrent events are not independent, only the first event during follow-up should be studied.

8 Research Question and Objectives

Primary objective: To assess the risk of prespecified adverse events << (list the AEs) >> following vaccination with <<specific COVID-19 vaccine product>>

Secondary objectives:

- To assess the risk of prespecified adverse events << (list the AEs) >> in specific vaccine groups defined by platform and/or components (e.g., adjuvant)
- To assess the risk of <<adverse events>> after COVID-19 vaccination by age at vaccination, race, sex, pregnancy status, <<comorbidities>>, <<infections>>, <<concomitant vaccinations>>, <<concomitant medications>>, and <<dose number>>

[Note: If a specific outcome is only relevant to specific subgroups (e.g., multiple inflammatory syndrome would only occur in children), the specific subgroups would be studied in the primary analysis].

[This protocol may be used to either study AESIs and/or unanticipated adverse events. If both AESIs and unanticipated adverse events are investigated, an alternative to the above designation of primary and secondary objectives is that the primary objectives would focus on unanticipated adverse events while the secondary objectives would focus on AESIs].

[The secondary analysis of vaccine groups defined by vaccine platforms or components will be done if the products are hypothesised to have a similar safety profile across the grouped products.]

[Not all objectives may be feasible to study at all sites, depending on data collection capabilities. Investigators may adapt the objectives based on local settings and specific adverse events. This may include the option to study adverse events, as additional safety data become available.]

Note to future investigators using this template as a starting point to develop a study protocol: the wording of some sections of this protocol can be retained as-is or modified as appropriate in a final study protocol. Notes directly to the investigators in these sections are indicated in square brackets. As there are multiple potential COVID-19 vaccine products under development and additional adverse events may be identified, this protocol template refers generically to a <<COVID-19 vaccine product>> and at times, <<adverse event>> which may be replaced with the name of the specific vaccines or adverse events being investigated. The language in some sections, however, describes general principles, issues, and considerations for the investigator and will require the investigator to develop those sections with study-specific content, as appropriate for the specific study being considered.

9 Research Methods

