9.2.2 Study Period

9.2.2.1 Self-controlled Risk Interval Design

A guiding principle for defining the study period for the SCRI design is that a full history of timing of both events and exposures must be available throughout the study period [3]. The study period will begin in each hospital when the vaccine becomes available in the catchment area for the hospital and will end on the last date on which data on vaccinations and hospital discharges is available.

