9.2.2.2 Case-Crossover and Vaccinated Case-Coverage Designs

For the CCO and vaccinated case-coverage designs, a full history of timing of exposures must be available in the risk and comparison windows preceding captured events. Therefore, the study period should comprise a period during which data on both exposures and outcomes are available.

For the CCO study, the study period should be selected to cover a time frame during which the propensity to receive the vaccine is relatively constant over time in the source population. If a such a study period is not available, the CCO design should not be used.

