9.2.3.2 Case-Crossover and Vaccinated Case-Coverage Designs

To be included as a case in the CCO or vaccinated case-coverage study, individuals must meet the following criteria. Note that the study population for analysis of each outcome of interest will be different.

- Meets criteria for the source population, assessed at the time of the event
- At least one occurrence of an event meeting case-identification criteria during the study period
- Data on exposures available through the beginning of comparison window

[figure not shown]
The follow-up period will begin at the start of the comparison window (that precedes the exposure window) and will finish at the date of outcome onset.

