9.2.5.2 Exposure Assessment in Cases

In this section, operational definitions for identifying exposure should be described, including type of vaccine codes.

Exposure status will be identified in confirmed and probable cases. For this study, an indicator for each dose of <<COVID-19 vaccine product>> and date of vaccination will need to be identified for all cases. In the SCRI design, if multiple doses of vaccine are given during the study period, each individual dose will be evaluated separately. To the extent feasible, in the case of multidose vaccines, exposure information should be captured following hospital discharge to avoid bias due to the outcome impacting the observation period for exposure. If collecting exposure information after hospital discharge is not possible, the impact of this potential bias could be explored in a sensitivity analysis using Farrington’s pseudolikelihood method for censored, perturbed, or curtailed postevent exposures [7].

In the primary analysis, exposure will be based on a specific COVID-19 vaccine product; a secondary analysis will be conducted stratified by vaccine groupings defined by technology, platform, or components (e.g., mRNA, adenovirus backbone, protein recombinant vaccines, adjuvant). If the concern for a particular outcome is related to a specific product (as per data existing at the time of full protocol development), the analysis for the particular outcome will only be conducted for the specific product, and a combined analysis of products will not be conducted.

Exposure information will be obtained from pharmacy dispensing records, general practice records, immunisation registers, vaccination cards, medical records, and/or other secondary data sources. The availability and feasibility of data sources to obtain vaccination information will likely vary by jurisdiction. Depending on the data source, vaccines may be identified via Anatomical Therapeutic Chemical codes, nationally used codes, local codes, or free text. If vaccination cards are used, and if feasible, a sample of vaccine records could be validated against other sources such as medical records or health care provider questionnaire to confirm the vaccine product and date of vaccination.

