Annex 5. Feasibility Questionnaire

General Questions

1. Name of data source: _____
2. Contact person: _____
Institution: _____
E-mail address: _____
Phone number: _____

Outcomes

3. Does your site have a hospital discharge database that captures diagnoses and procedures?
___ Yes
___ No → Stop, thank you for your time
4. Does your site distinguish primary diagnoses from the other diagnoses?
___ Yes
___ No
5. Number of patients treated by your hospital annually:

6. Number of patients treated by your hospital annually for the following outcomes:
 - a. [Outcome A]: _____
 - b. [Outcome B]: _____
 - c. etc
7. What is the geographic area covered in the catchment area for your hospital?

8. What is the population coverage of your hospital?

9. How often are your hospitalisation data refreshed and made available for research?

10. How long is the data lag of the hospitalisation records, that is, how much time passes after hospitalisation before the data are available for research purposes?

11. What is the earliest date of data captured by your hospitalisation data?

12. Are the calendar dates of the hospitalisation available?

Yes, the admission and discharge date are available

Yes, the diagnosis date is available

Yes, other. Please specify: _____

13. Can your site identify diagnoses made in the hospital setting of the following outcomes?

a. [Outcome A]? Yes No

b. [Outcome B]? Yes No Etc.

14. What coding system does your site use for diagnosis in the hospital setting?

15. Does your site have the ability to validate outcomes and dates of outcome onset through the use of medical record review, physician questionnaires, case notes, or other methods?

Yes

No

16. What method can you use to validate outcomes and date of onset?

Medical record review

Physician questionnaire

Case notes

Other, please specify: _____

Exposure

17. Can your site identify receipt of COVID-19 vaccines through linkage with other data?

Yes

No → Stop, thank you for your time.

Note that for this study, primary data collection or other self-report information on vaccinations is not acceptable.

18. To what type of exposure data does your site have access (check all that apply)?

Vaccine registry

Primary care records

Pharmacy dispensing data

Patient vaccination cards

Hospital-based medical records

Other, please specify: _____

19. What is the population coverage of the vaccination data source?

20. What is the geographic area covered by the vaccination data source?

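### Section 7 says that using only vaccinated cases avoids bias from incomplete vaccination data, but this holds only if recording a dose does not depend on the time from vaccination to event

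*Protocol*

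**What the plan says.** Section 7 (Rationale and Background) says of the SCRI and CCO that only vaccinated people with an event inform the risk estimate, "thereby avoiding bias due to exposed persons being wrongly classified as unexposed because the data source for vaccinations is incomplete". The statement carries no condition.

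Section 9.2.5.2 sets the exposure sources: "Exposure information will be obtained from pharmacy dispensing records, general practice records, immunisation registers, vaccination cards, medical records, and/or other secondary data sources". It gives no order of preference. Section 9.3 also lists medical records among the data sources, and item 18 of the feasibility questionnaire (Annex 5) has a box for "Hospital-based medical records".

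Other provisions ask for completeness:

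- Section 9.2.2.1, for the SCRI: "a full history of timing of both events and exposures must be available throughout the study period".
- Section 9.2.2.2, for the vaccinated case-coverage design and the CCO: "a full history of timing of exposures must be available in the risk and comparison windows preceding captured events".
- Section 9.2.3.2, as an inclusion criterion for those two designs: "Data on exposures available through the beginning of comparison window".
- Annex 5, item 17, stops a site that answers no to "Can your site identify receipt of COVID-19 vaccines through linkage with other data", and adds that "primary data collection or other self-report information on vaccinations is not acceptable".

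Exposure validation in section 9.2.5.2 is optional, covers a sample, applies only where vaccination cards are used, and may itself use medical records as the comparator. Neither the sensitivity analyses (9.6.5) nor the limitations (9.8) mention capture that differs between windows. Section 9.8 says only that the validity of vaccine codes and dates is unknown.

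**The concern.** In a case-only analysis an unrecorded dose does not move a case into an unexposed comparison group. It removes the case. That is harmless if cases are lost equally from both windows. It biases the estimate if they are lost more often from one.

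A hospital record is a source where equal loss is doubtful. A dose given shortly before admission for an acute event may well be asked about and noted, and one given two or three months before may not be. The protocol's own illustrations in section 9.2.5.3 set such doses against each other: 1 to 21 against 50 to 70 days before the event (CCO), and 1 to 42 against 43 to 127 days after vaccination (SCRI). The blinded adjudication and the separate vaccination eCRF (sections 9.2.5.1 and 9.2.4) act after the record has been written, so they cannot restore a dose that was never noted.

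What is at stake is a spurious association, or a masked one if capture runs the other way. The template is aimed at places without population-based registers, where reliance on charts would be greatest. Because section 7 tells its users that the design already deals with incomplete exposure data, they have little reason to check.

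**Working it through.** **Inputs.** From the protocol: Annex 3, by which a CCO case is informative only if vaccinated in exactly one window; and Table 3 (section 9.4), 50% rows, with 194 cases for relative incidence 1.5 and 69 for relative incidence 2. Assumed, because the protocol gives no capture rates: s1 and s0. Also assumed: a two-sided 5% level (Table 3 states none, but section 9.6.2 uses 95% intervals), one relevant dose per case, and all exposure taken from the source in question.

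**Table 3 first.** The signed-root likelihood-ratio formula for case series is n = (1.96 + 0.8416·√B)²/A. Here r is the share of time at risk, b = ln RI, p = RI·r/(RI·r + 1 − r), A = 2[p·b − ln(RI·r + 1 − r)] and B = (b²/A)·RI·r(1 − r)/(RI·r + 1 − r)².

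- r = 0.5, RI = 1.5: A = 0.04027, B = 0.9798, n = 193.7, rounded up to 194.
- r = 0.5, RI = 2: A = 0.11327, B = 0.9426, n = 68.1, rounded up to 69.

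All 15 cells reproduce at two-sided 5% and 80% power, so Table 3 is not in dispute.

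**Bias.** Let N1 informative cases truly be vaccinated in the risk window and N0 in the control or comparison window. The analysis sees s1·N1 and s0·N0, so

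apparent ratio = (s1·N1)/(s0·N0) = (s1/s0) × true ratio.

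The same factor applies to the SCRI rate ratio, because the time offset cancels. Incomplete capture is therefore harmless if and only if s1 = s0; 0.90/0.90 and 0.60/0.60 both give 1.00.

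**Size with no true effect and equal windows.** The share of recorded cases in the risk window is p = k/(1 + k), with k = s1/s0. It is tested against 0.5 with an exact two-sided 5% binomial test. The critical values are 112 or more, or 82 or fewer, of 194; and 44 or more, or 25 or fewer, of 69.

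| Assumed s1/s0 | Ratio k | p | Rejection, n = 194 | Rejection, n = 69 |
|---|---|---|---|---|
| equal | 1.00 | 0.500 | 3.7% | 2.9% |
| 0.95/0.85 | 1.12 | 0.528 | 9.7% | 4.7% |
| 0.95/0.70 | 1.36 | 0.576 | 51% | 18% |
| 0.90/0.60 | 1.50 | 0.600 | 76% | 31% |

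The exact test is conservative, so the equal-capture row is the right baseline. More cases make the error more likely, because the bias stays while the interval narrows. If earlier doses were the better recorded, say 0.60/0.90, the apparent ratio would be 0.67 and a real risk could be hidden.

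**Vaccinated case-coverage.** The section 7 sentence does not cover this design. Its offset is the expected odds in a reference population. If the reference comes from a register with even capture and case exposure comes from charts, s1/s0 enters the case side only and the odds ratio is multiplied by the same factor.

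**The case against.** The strongest reply is that the protocol already forbids the situation. It demands a full exposure history in the windows, makes exposure data back to the start of the comparison window an inclusion criterion, screens out sites without linkage, and rejects self-report. An admission note resting on the patient's account is arguably self-report. Annex 5 also asks about coverage, lag, care settings, earliest date and exactness of dates. If these requirements were truly met, there would be no differential loss. This stands as far as it goes. But an unmentioned dose in a chart looks the same as no dose, nothing says how completeness by window is to be shown, and item 18 still offers hospital records. Section 7 also weakens the full-history rules by suggesting that incompleteness is handled by design.

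A reader might infer that charts do record recent doses better and so create a false signal. The protocol does not say this. It is a plausible assumption of unknown size. Nor does the protocol name the record of the index admission, or accept any chart as sole source. The section 7 sentence concerns one mechanism and two designs; it does not say that incomplete data can never cause bias.

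The example windows are illustrative, and one SCRI example sets 0 to 7 against 8 to 15 days, where a recency difference would be much weaker. The larger rejection rates need capture gaps of 25 to 30 percentage points across all informative cases. With 69 cases and 0.95/0.85 the rate stays below the nominal 5%.

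Finally, this is a template, and the choice of sources may be left to the investigator. That argues against a rigid rule on sources. It does not rescue an unqualified statement in the rationale.

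**Conclusion.** The point holds as a missing condition and an unguarded route to bias. The protection described in section 7 exists only when capture does not vary with the time between vaccination and event. The protocol admits a source where that is doubtful, and it provides neither a check by window nor a sensitivity analysis for it.

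The multiplier s1/s0 follows from the design. Its value is unknown: 1.12 to 1.50 over the assumed range, and exactly 1 with equal capture. The rejection rates illustrate those assumptions and do not predict what a study would find. The documents do not support concluding that the designs will produce false signals, or that chart-only cases must be barred from the primary analysis. Barring them would be a trade-off in a template meant for sites without registers.

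**What to change.** 1. **Section 7:** state that incomplete vaccination data are harmless only if the chance of recording a dose is unrelated to the time between vaccination and event. Reconcile this with the full-history requirements in sections 9.2.2.1, 9.2.2.2 and 9.2.3.2.
2. **Section 9.2.5.2:** give priority to sources recorded independently of the event (register, general practice record, dispensing record, vaccination card), searched across both windows for every case. Record the source used in the vaccination eCRF.
3. **Section 9.6.5:** add a sensitivity analysis restricted to cases whose exposure comes from an event-independent source.

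The cost is some wording, one eCRF field and one further analysis with fewer cases and therefore less precision. Sites that depend on charts can still contribute to the primary analysis.
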